### 16.1.9 Documentation of Statistical Methods

Receptos, Inc.  
Protocol RPC01-201

Statistical Analysis Plan – Part A, V1.2  
Date Issued: May 20, 2014

the End of Study/Early Withdrawal page on the CRF. If the last dose date on the End of Study/Early Withdrawal page is missing or a subject is lost to follow-up, but the drug accountability log confirms that the subject has taken study drug, the visit date following the last completed drug accountability log will be used.

The extent of exposure and study drug exposure will be summarized in a table by summary statistics for the Safety Population.

The listing will present subject data for the first dose date, last dose date, extent of exposure, and study drug exposure.

#### 8.2.2 Treatment Compliance

Study drug compliance will be calculated for each subject by taking into account whether a subject takes all doses of study drug as instructed. The study drug compliance rate will be summarized by treatment group using descriptive statistics for the Safety Population. The overall study drug compliance rate will be calculated by dividing the total number of capsules taken at all visits by the total number of capsules prescribed for all visits based upon the duration in the study and then multiplying by 100. The number and percentage of subjects in each compliance rate category (<=50%, 51-60%, 61-70%, 71-80%, and 81-100%, >100%, <80%, and >120%) will be reported. Percentages will be calculated out of the number of subjects who have been dosed in the study period.

## 9 Efficacy Analysis

Analysis of all efficacy endpoints will primarily be based on the ITT population. Additionally, the primary and secondary clinical efficacy endpoints will also be analyzed based on the PP population. All sensitivity analyses will only be conducted in the ITT population. The primary analysis of each efficacy endpoint will also be repeated using only the subset of observed data; i.e., without imputation for missing results. Listings will be provided for efficacy endpoints.

### 9.1 Primary Efficacy Endpoint

The primary efficacy endpoint of Part A is the total number of GdE lesions, assessed on brain MRIs from Week 12 to Week 24.

#### 9.1.1 Primary Analysis

##### *Missing data*

A method of last observation carried forward (LOCF) will be used for subjects with missing post baseline lesions. If a subject is missing only 1 or 2 consecutive post-baseline scans, then the last valid non-missing, post-baseline observation will be carried forward to impute the missing value. However, if there are no post-baseline values to be carried forward or if the subject is missing more than 2 consecutive scans, then the mean

### 16.1.9 Documentation of Statistical Methods

Receptos, Inc.  
Protocol RPC01-201

Statistical Analysis Plan – Part A, V1.2  
Date Issued: May 20, 2014

number of lesions from subjects in the same treatment group at the same visit will be used as the imputed value.

#### *Analysis method*

The total number of GdE lesions from Week 12 to Week 24 will be compared between each RPC1063 group and the placebo group using the stratified Wilcoxon-Mann-Whitney test, stratified by presence of GdE lesions at baseline (absent or present). This comparison will be assessed using a 2-sided test at the alpha=0.04944 level of significance (to keep the overall Part A level of significant at alpha=0.05, accounting for the O'Brien-Fleming adjustment and interim analysis) (Reboussin, 2000).

#### **9.1.2 Sensitivity Analysis**

The first sensitivity analysis will be using a negative binomial regression model to test the total number of GdE lesions, adjusting for the baseline number of GdE lesions and region. The results of the model are estimated as the log of the number of total GdE lesions, which will be exponentiated to present the adjusted mean number of lesions in each treatment group. The 95% confidence intervals of the mean number of total GdE lesions in each treatment group will be presented to further summarize the data.

Since corticosteroids may have a short term effect on GdE lesions, the second sensitivity analysis will be excluding MRI scans obtained with 24 days of steroid treatment. For this analysis, scans obtained within 24 days of the start date of steroid treatment will be considered missing and an imputed value, rather than the actual value, will be used in the calculation. Qualifying corticosteroids will be those with the ATC Level 2 terms of “CORTICOSTEROIDS FOR SYSTEMIC USE”.

Summary statistics on the number of GdE lesions at Baseline and each visit will be reported, along with the change from Baseline and the percent change from Baseline. In addition, the proportion of subjects with 0, 1, 2, 3, 4, and  $\geq 5$  at Baseline and each visit will be reported.

#### **9.2 Key Secondary Efficacy Endpoints**

The key secondary efficacy endpoints of Part A are:

- The number of GdE lesions at Week 24
- Total number of new or enlarging hyperintense T2-weighted brain MRI lesions from Week 12 to Week 24
- ARR at the end of Week 24

#### **9.2.1 Analyses**

## 16.1.9 Documentation of Statistical Methods

Receptos, Inc.  
Protocol RPC01-201

Statistical Analysis Plan – Part A, V1.2  
Date Issued: May 20, 2014

### **Secondary Endpoint: The number of GdE lesions at Week 24**

The number of GdE lesions at Week 24 will be analyzed using the stratified Wilcoxon-Mann-Whitney test, stratified by presence of GdE lesions at baseline (absent or present). A sensitivity analysis will be using a negative binomial regression model, adjusted for the baseline number of GdE lesions. Missing GdE data values will be imputed using the mean from subjects of the same treatment group at the same visit.

The proportion of subjects who are GdE lesion free at Week 24 will be analyzed using Fisher's Exact test. Missing Week 24 GdE lesion data will be handled via LOCF. A sensitivity analysis will be conducted using the non-responder imputation method. For this analysis, any subject missing their Week 24 GdE lesion data will be counted as having 1 or more lesions at Week 24 (i.e., will be considered "not GdE lesion free" for this analysis).

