13.6. Statistical Methods

13.6.1. Missing Data

Part A

Last observation carried forward (LOCF) and mean imputation will be used for patients with missing post-baseline lesions. If a patient is missing at most 2 post-baseline scans, then the last non-missing, post-baseline observation will be carried forward to impute the missing value.

However, if there are no values to be carried forward or if the patient is missing more than 2 scans, then the mean number of lesions from patients in the same treatment group at the same visit will be used as the imputed value. Sensitivity analyses will be specified in the SAP.

Part B

Sensitivity analyses will be specified in the SAP.

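### SAP 9.2.1 fills every missing Week 24 GdE count with the arm mean, while Protocol 13.6.1 and SAP 9.1.1 first carry the last scan forward, so the first-ranked Part A key secondary can give a different verdict depending on the rule used

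*SAP*

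**What the plan says.** Four places in the documents deal with a missing Part A lesion count.

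- **Protocol 13.6.1, Part A.** This covers missing post-baseline lesion data without naming an endpoint: "If a patient is missing at most 2 post-baseline scans, then the last non-missing, post-baseline observation will be carried forward". The same-arm, same-visit mean is only the fallback: "if there are no values to be carried forward or if the patient is missing more than 2 scans, then the mean number".
- **SAP 9.1.1 (primary total, Weeks 12 to 24).** Almost the same rule, but counted in consecutive scans: "If a subject is missing only 1 or 2 consecutive post-baseline scans, then the last valid non-missing, post-baseline observation will be carried forward". The arm mean again applies only when nothing can be carried forward or more than 2 consecutive scans are missing.
- **SAP 9.2.1, Week 24 GdE count.** "The number of GdE lesions at Week 24 will be analyzed using the stratified Wilcoxon-Mann-Whitney test", stratified by baseline GdE presence. For missing values: "Missing GdE data values will be imputed using the mean from subjects of the same treatment group at the same visit".
- **SAP 9.2.1, lesion-free proportion, next paragraph under the same heading.** "Missing Week 24 GdE lesion data will be handled via LOCF".

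SAP 9.2.1 also uses the mean-only rule for the new or enlarging T2 count, the second-ranked key secondary. SAP section 5 tests the secondaries in rank order once the primary comparisons are significant. SAP section 9 repeats each primary analysis on observed data only.

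**The concern.** One scan enters three Part A analyses, and no reason is given for treating it differently in one of them. The mean-only rule discards the patient's own recent scan and gives all missing patients in an arm the same arm-specific value. The rank test then sees a tied block whose position is set by the arm's own result, and treats it as independent observations. This can push the test above its nominal level. The endpoint opens the secondary sequence, so the T2 and ARR tests depend on its outcome.

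The point is confined to patients for whom a carried-forward value exists and is ignored. Where none is available, the count rules all give the arm mean and do not conflict.

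**Working it through.** **1. The plan's own figures.** Noether's formula is n = (z₀.₉₇₅ + z₀.₈₀)² / [6(P − 0.5)²]. With P = 0.65 this is (1.960 + 0.842)² / (6 × 0.0225) = 58.14, so 59 per group. Allowing for dropout, 59/0.85 = 69.4, so 70 per arm and 3 × 70 = 210. O'Brien-Fleming-type spending at information fraction 0.45 gives 0.00167 and 0.04944. All match the documents. The inputs taken forward are 70 per arm and 15% dropout.

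**2. The rules side by side.** Post-baseline scans fall at Weeks 8, 12, 16, 20 and 24. The cells show the Week 24 value each analysis would use.

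| Scans missing | Primary total | Key secondary count | Lesion-free |
|---|---|---|---|
| 24 only | Week 20 value | arm mean | Week 20 value |
| 20, 24 | Week 16 value | arm mean | Week 16 value |
| 16, 20, 24 | arm mean | arm mean | Week 12 value |
| 8, 16, 24 | Protocol: arm mean (3 missing). SAP 9.1.1: most naturally Week 20 value (no run over 2) | arm mean | Week 20 value |

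Rows 1 and 2 are the conflict. Row 3 shows that carry-forward in the lesion-free analysis has no limit on missing scans. Row 4 shows where the Protocol and SAP 9.1.1 part company.

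**3. Effect on the test.** The statistic is the van Elteren form: Σ wₛ(Wₛ − E Wₛ) / √(Σ wₛ² Var Wₛ), wₛ = 1/(Nₛ + 1), over the two baseline-GdE strata, two-sided at 0.05. The documents give no lesion distribution, so the following are assumptions: gamma-Poisson counts, missing completely at random.

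*Setting A.* Only Week 24 is missing, in 10 of 70 patients per arm (14%). Placebo mean is 1 or 2 per scan, shape 0.5. There were 6,000 trials for the null and P = 0.58, and 1,500 for P = 0.65 and 0.75.

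*Setting B.* 15% have no Week 24 scan: either all are dropouts spread over the scans, or 10% are dropouts and 5% miss Week 24 only. Mean is 1.0 (shape 0.5) or 2.5 (shape 0.4). There were 3,000 to 4,000 trials.

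| Null rejection, test taken alone | Setting A | Setting B |
|---|---|---|
| SAP 9.2.1 mean rule | 11.0-14.6% | 12-18%, up to 20% in a repeat |
| Carry-forward / Protocol rule | 4.7-4.8% (about 5-6% across runs) | 7-11% |
| Complete data | – | 4-6% |

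Monte Carlo error in Setting A is small: √(0.146 × 0.854/6000) = 0.5 percentage points at the highest figure. With 1 missing scan per arm, the mean rule gives 5.0-5.5%.

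**4. How often the verdict differs.**

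| Truth | Trials in which the two rules disagree |
|---|---|
| Null, 10 missing per arm (A) | 8-12% |
| P = 0.58, 10 missing per arm (A) | 16-17% |
| Rate reduction 40-50% (B) | 10-14% |
| P = 0.65 set in Setting A (rate ratios 0.152/1.0 = 0.15 and 0.499/2.0 = 0.25) | under 1% |
| P near 0.65 on the primary total (rate ratio 0.3) | 2-6% |
| P near 0.75 | 0-0.3% |

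Disagreement runs both ways. At P = 0.58 with mean 1.0, 6.5% of trials were significant only under carry-forward and 9.2% only under the mean rule.

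**5. With the gate.** Requiring the primary 1 mg comparison to be significant at 0.04944 as well, the mean rule rejected in 2.9-4.3% of null trials (1,200 per setting; about 2-5% across runs).

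**The case against.** The strongest case is that the operative rule is not in doubt. SAP 5.4.4 says imputation is set endpoint by endpoint, Protocol 13.3 lets the SAP add detail, and SAP 9.1.1 sits under the primary endpoint. A programmer would follow SAP 9.2.1, and the observed-data repeat gives a check. That much stands: the analysis can be run as written. It does not explain why the SAP departs from a general Protocol rule. Nor does it make the arm-mean test hold its level, and the observed-data repeat does not settle which imputed result governs the sequence.

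Three stronger readings are tempting and are not supported.

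- *That Part A carries an 11-20% type I error.* SAP section 5 tests this endpoint only after a significant primary, and the joint null rate is about 2-5%. A null Week 24 count beside a true effect on a total that includes Week 24 is an unlikely case.
- *That the test result changes.* It can change. At the planned P = 0.65 it does so in a few percent of trials or fewer, and with one missing scan per arm in 1.5% (null) to 4.8% (P = 0.58).
- *That all the excess comes from skipping carry-forward.* In Setting B the Protocol rule itself rejects at 7-11%, because patients missing more than 2 scans still receive the arm mean. Setting A isolates the part at issue here.

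**Conclusion.** The conflict is a stated rule, not a missing detail. For a patient missing only Week 24, or Weeks 20 and 24, SAP 9.2.1 gives the first-ranked key secondary a different value from the one the same scan has in the primary total and the lesion-free analysis. Taken alone, the mean-only test rejects a true null in about 11-20% of trials when about 15% of Week 24 scans are missing, against about 5-6% under carry-forward when only Week 24 is missing, or 7-11% with dropouts who still get the fallback.

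These rates rest on assumed gamma-Poisson counts and missingness at random. They shrink to near nominal if very few scans are missing. The practical exposure is largest at weak to moderate effects and small at the planned effect. It should be corrected because correction is cheap and follows the sponsor's own Protocol; it does not threaten the primary result.

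**What to change.** 1. In SAP 9.2.1, replace the mean-only sentence for the Week 24 GdE count with the Protocol 13.6.1 rule: carry the last post-baseline scan forward when at most 2 scans are missing, with the arm mean only as the fallback.
2. Choose one trigger, at most 2 missing or 1 or 2 consecutive missing, and use it in both Protocol 13.6.1 and SAP 9.1.1.
3. Apply the same rule to the T2 count in SAP 9.2.1, or state why it differs.
4. Keep the observed-data analysis as the check.

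This gives the Week 24 count one value in the primary total and the key secondary. The lesion-free analysis will match only if its carry-forward is given the same limit; otherwise a patient with 0 at Week 12 who then drops out is still lesion free in one analysis and holds the arm mean in the other.

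The cost is one replaced SAP sentence and the alignment edits, before database lock. No new data are needed. If Part A has already been unblinded, report both rules side by side.

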8.1.2. Secondary Study Objectives

Part A

- To assess the proportion of patients who are free of GdE lesions at Week 24
- To assess the effect of RPC1063 on the cumulative number of new/enlarging T2 lesions from Week 12 to Week 24
- To compare the clinical efficacy of RPC1063 to placebo in patients with RMS as assessed by reduction in annualized relapse rate (ARR) and proportion of relapse free patients at Week 24
- To assess the safety and tolerability of RPC1063 in patients with RMS
- To assess the pharmacokinetics (PK) and PD of RPC1063 in patients with RMS

Part B

- To assess the effect of RPC1063 on the proportion of patients with new/enlarging T2 lesions at Month 24
- To evaluate whether the efficacy of RPC1063 is superior to IFN β -1a in delaying the accumulation of disability, as assessed by the Multiple Sclerosis Functional Composite (MSFC), and visual function as measured by the low contrast visual acuity test (LCLA) (Balcer, 2000).
- To evaluate whether the efficacy of RPC1063 is superior to IFN β -1a in delaying the accumulation of disability, as assessed by the Expanded Disability Status Scale (EDSS)
- To assess the effect of RPC1063 on brain atrophy over 24 months
- To evaluate the effect of RPC1063 on patient-reported quality of life as assessed by the Multiple Sclerosis Quality of Life-54 (MSQOL-54)
- To assess the safety and tolerability of RPC1063 in patients with RMS

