13.6.4. Efficacy

Part A

For the primary analysis, the cumulative number of GdE lesions from Week 12 to Week 24 will be compared between the 1 mg RPC1063 group and the placebo group using the stratified Wilcoxon-Mann-Whitney test, stratified by presence of GdE lesions at baseline (absent or present). This comparison will be assessed using a 2-sided test at the $\alpha=0.04944$ level of significance (to keep the overall Part A level of significant at $\alpha=0.05$, accounting for the O'Brien-Fleming adjustment and interim analysis) (Reboussin, 2000). If the comparison between the 1 mg RPC1063 group and placebo is statistically significant, then a second primary analysis will similarly compare the 0.5 mg RPC1063 group and the placebo group, also based on a 2-sided test at the $\alpha=0.04944$ level of significance. Sensitivity and descriptive analyses will also be presented.

The secondary endpoint of the proportion of patients free of GdE lesions at Week 24 will be analyzed using a logistic regression model with treatment group (three levels) and presence of baseline GdE lesions (absent, present) as factors. Pairwise comparisons between the 1 mg RPC1063 group and placebo, and between the 0.5 mg RPC1063 group and placebo, will be tested.

Quantitative endpoints such as the percent brain volume change over 24 weeks will be analyzed using analysis of covariance models with treatment group as a factor and the baseline value of the corresponding parameter as a covariate.

Endpoints that are defined in terms of lesion counts will be analyzed using the Wilcoxon-Mann-Whitney test. These analyses will include only the two groups being compared.

All secondary endpoints will be analyzed using 2-sided tests at the 5% level of significance.

Part B

The primary analysis for the ARR will be carried out using a Poisson regression model. The model will compare treatment groups, adjusted for region, age, and the number of GdE lesions at baseline. To account for multiple comparisons, each of the 2 treatment comparisons with IFN β -1a will be tested at the $\alpha = 0.025$ level. Results will be summarized by randomized treatment group and expressed as unadjusted and adjusted relapse rates, odds ratios, corresponding 95% confidence intervals, and p-values.

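### Protocol 13.6.4 and SAP 9.2.1 prescribe different analyses of the Part A proportion free of GdE lesions at Week 24, and the SAP's unadjusted Fisher test is usually the less powerful

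*SAP*

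**What the plan says.** Protocol 8.1.2 lists this first among the Part A secondary objectives: "To assess the proportion of patients who are free of GdE lesions at Week 24".

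Protocol 13.6.4 sets the method: "The secondary endpoint of the proportion of patients free of GdE lesions at Week 24 will be analyzed using a logistic regression model", with treatment at three levels and "presence of baseline GdE lesions (absent, present) as factors". Each dose is then compared with placebo. The same section adds: "All secondary endpoints will be analyzed using 2-sided tests at the 5% level of significance".

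SAP 9.2.1 gives a different method: "The proportion of subjects who are GdE lesion free at Week 24 will be analyzed using" Fisher's exact test. Missing Week 24 data are carried forward, and one sensitivity analysis counts missing patients as not lesion-free. No baseline-adjusted analysis of the proportion remains, and no reason for the difference is stated.

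Immediately before that, in the same subsection, the SAP says: "The number of GdE lesions at Week 24 will be analyzed using the stratified Wilcoxon-Mann-Whitney test, stratified by presence of GdE lesions at baseline". It applies the same stratification to the primary endpoint (9.1.1) and to the T2 lesion endpoint (9.2.1). Its relapse-rate model includes presence of GdE lesions, without naming the time point.

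The ranked key secondary endpoint in both documents (Protocol 8.2.1, SAP 4.2) is the number of GdE lesions at Week 24, not the proportion of patients without any.

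**The concern.** Two prespecified methods are in force for one quantity, so the reported p-value and effect estimate depend on which document the analyst follows. Protocol 13.3 expects the SAP to add detail to the protocol's methods, and a different test goes beyond that.

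The SAP's choice also departs from its own practice. Baseline GdE presence is used for the primary endpoint and for the three ranked secondary endpoints, but not here. Randomization in Part A is stratified by country only, so the design does not balance baseline GdE status between arms of about 70.

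What is at stake is power and consistency for a secondary objective. There is no risk of inflated type I error, because Fisher's test errs on the conservative side.

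**Working it through.** **1. The plan's own sample size.** The only Part A power figure concerns the primary endpoint (Protocol 13.2, SAP 5.1). Noether's formula at two-sided 5% and 80% power, with P = 0.65, is

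N = (1.960 + 0.842)² / (12 × 0.25 × 0.15²) = 7.849 / 0.0675 = 116.3 in total, or 58.1 per arm.

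The plan's 59 per arm is reproduced, and 59 / 0.85 = 69.4 gives the planned 70. The documents state no power for the lesion-free proportion.

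**2. Inputs for the proportion.** Taken from the documents: 59 evaluable or 70 enrolled per arm, and a two-sided 5% level. Assumed, because the documents are silent: the share of patients with baseline lesions, the placebo lesion-free rate without and with baseline lesions (written absent/present), and the odds ratio for being lesion-free, taken as equal in both strata.

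Example with 0.7/0.4, 40% with baseline lesions and odds ratio 3:
- Baseline absent: odds 0.7/0.3 × 3 = 7, so 0.875 on active.
- Baseline present: odds 0.4/0.6 × 3 = 2, so 0.667 on active.
- Overall: placebo 0.6 × 0.7 + 0.4 × 0.4 = 0.58; active 0.6 × 0.875 + 0.4 × 0.667 = 0.79. The difference is about 21 points.

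**3. Fisher against a stratified test.** Power in 20,000 simulated two-arm trials per setting, 70 per arm, 40% with baseline lesions:

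| Placebo rates | Odds ratio | Fisher | CMH | Loss (points) |
|---|---|---|---|---|
| 0.7/0.4 | 2.5 | 57.5% | 66.7% | 9.2 |
| 0.7/0.4 | 3 | 72.5% | 80.6% | 8.1 |
| 0.8/0.3 | 2.5 | 42.5% | 58.8% | 16.3 |
| 0.8/0.3 | 3 | 57.1% | 73.9% | 16.8 |

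With no treatment effect, Fisher rejected in 3.2% of trials and CMH in 4.8%. With 59 per arm the losses in these settings are similar, about 9 to 17 points.

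**4. Where the loss comes from.** An unadjusted Pearson test separates the two causes. Fisher to Pearson is conservatism; Pearson to the adjusted test is the covariate. All rows use 70 per arm.

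| Setting | Fisher | Pearson | Adjusted | Conservatism | Covariate |
|---|---|---|---|---|---|
| 0.6/0.6, odds ratio 3 | 77.6% | 82.7% | 82.2% (logistic, Wald) | 5.1 | −0.5 |
| 0.7/0.4, 40%, odds ratio 2.5 | 56.4% | 63.2% | 66.1% (CMH) | 6.8 | 2.9 |
| 0.7/0.4, 40%, odds ratio 3 | 73.1% | 78.8% | 81.2% (CMH) | 5.7 | 2.4 |
| 0.8/0.3, 50%, odds ratio 3 | 60.3% | 66.1% | 76.4% (logistic, Wald) | 5.8 | 10.3 |

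The 0.7/0.4 rows come from a separate run of 6,000 trials, so they differ slightly from step 3. In the first row baseline status predicts nothing, so its prevalence does not matter; the loss is 82.2 − 77.6 = 4.6 points, all of it conservatism. That is the low end of the range.

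**5. How far the loss moves (70 per arm).**
- Larger effects, 40% with baseline lesions: under 0.7/0.4 it is 93.6 − 88.7 = 4.9 points at odds ratio 4 and 99.2 − 97.9 = 1.3 at odds ratio 6. Under 0.8/0.3 it is 97.9 − 92.7 = 5.2 at odds ratio 6.
- Stronger covariate (0.85/0.2), odds ratio 3, logistic Wald test: 59.5 − 35.6 = 23.9 points with 30% baseline lesions and 68.1 − 42.4 = 25.7 with 50%.

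**The case against.** The strongest case against has four parts.

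- **Size.** A reader might infer a fixed loss of about 8 to 17 points. That describes two assumed prognostic patterns at odds ratios of 2.5 to 3. If the design value P = 0.65 is carried over to a binary outcome (itself an assumption), the difference is 2 × (0.65 − 0.5) = 30 points. Fisher then has at least 92% power, and the loss against a likelihood-ratio test is about 0 to 5 points. This stands: the figure must be given as conditional.
- **Cause.** A reader might blame the missing covariate for the whole loss. Under 0.7/0.4 it accounts for only about 2 to 3 of 8 to 10 points. That baseline GdE strongly predicts later lesion-free status is not shown in either document. This stands too, although the proposed change removes both causes.
- **Importance.** A reader might think a step of the testing hierarchy depends on Fisher's test, because SAP 9.2.1 places the proportion under the heading of the first ranked endpoint. The ranked quantity is the count, which is stratified by baseline GdE, and SAP section 5 takes its order from Protocol 8.2, which does not list the proportion for Part A. SAP section 5 also names baseline GdE presence as a subgroup factor, though that is not an adjusted test. This limits the weight of the point.
- **Sequence.** A reader might infer that the SAP discarded the protocol's method. SAP V1.2 is dated 20 May 2014 and the supplied protocol, Version 4.0, is dated 1 October 2014, so the order of change cannot be established. The later document still carries the adjusted model, so the conflict remains.

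**Conclusion.** The conflict is certain and can be read directly from the two sections. Its effect on power is conditional. Over placebo patterns from 0.6/0.6 to 0.8/0.3, with 59 to 70 per arm, 40% with baseline lesions and an odds ratio of 2.5 to 3, the SAP's test costs about 5 to 17 points. About 6 to 8 of these are Fisher's conservatism, slightly fewer at the low end, where they are the whole loss. Outside those assumptions the cost runs from near zero to more than 20 points. The simulations compare two arms, whereas the protocol's model has three treatment levels.

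Fisher's test is valid, so nothing here threatens type I error. This is a worthwhile correction to an unranked secondary analysis and does not bear on the trial's main conclusions.

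**What to change.** In SAP 9.2.1, make the main analysis of the Week 24 lesion-free proportion the protocol's logistic model (treatment group; baseline GdE absent or present), or a CMH test stratified by baseline GdE presence. Keep Fisher's exact test as a sensitivity analysis. If the logistic model is used, name the test statistic: with a 30-point difference the Wald test was up to about 4 points less powerful than Fisher in some settings, while the likelihood-ratio test was not. If the CMH test is preferred, or Fisher is kept as the main analysis, record the reason and align Protocol 13.6.4.

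The cost is about one line of SAP text. Baseline GdE status is already collected and already used for stratification, so no new data are needed.
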